### 5.2.2 Definition of Dose-Limiting Toxicity

A DLT is defined as any grade  $\geq 3$  adverse event that is at least possibly, probably or definitely related to ipilimumab during the DLT period, unless judged by the treating Investigator to be more likely related to underlying tumor, concurrent medication or co-morbid event. The DLT period is considered the first 42 days of study therapy and will include labs and other evaluations taken at the end of six weeks of study therapy. Events that are considered unlikely related to ipilimumab, but at least probably related to radiation therapy will not be considered a DLT.

The following exceptions will not be classified as DLT:

- Grade 3 Immune-related adverse events (irAEs – see definition below) that downgrade to Grade  $\leq 2$  within 5 days, or to Grade  $\leq 1$  or baseline within 14 days after onset of the event, whereby maximal supportive care, including systemic corticosteroids, is permitted.
- Grade 3 asymptomatic endocrinopathy, managed with or without systemic corticosteroid therapy and/or hormone replacement therapy.
- Grade 3 inflammatory reaction attributed to a local antitumor response (e.g., inflammatory reaction at sites of metastatic disease, lymph nodes, etc).
- Grade 2 pneumonitis, neurological event, or uveitis that downgrades to Grade  $\leq 1$  within 3 days, whereby maximal supportive care is permitted.
- Liver transaminase elevation  $\leq 8$  times ULN.
- Total bilirubin  $\leq 5$  times ULN.
- Any pre-existing lab abnormality that deteriorates to Grade 3/4, but where the increment of deterioration is considered not clinically significant by Investigator, overall study Principal Investigator and sponsor.

DLT will also include grade 2 immune-related adverse events that occur during the DLT period defined above that require interruption of ipilimumab and do not improve to grade  $\leq 1$  with appropriate supportive care and symptomatic treatment with 7 days.

Immune-related adverse events (irAEs) are defined as AEs of immune nature (i.e., inflammatory) in the absence of a clear alternative etiology. In the absence of clinical abnormality, repeat laboratory testing will be conducted to confirm significant laboratory findings prior to designation as a DLT.

While rules for adjudicating DLTs are specified above, an AE of Grade  $< 3$  (except if listed as exempt above), may also be defined as a DLT after a consultation with the Sponsor and the overall study Principal Investigator, based on the emerging safety profile of ipilimumab.

Patients who experience DLT may be discontinued from study therapy and will enter the post-study follow-up phase of the study (see Section 5.7) or participants who have fully recovered from

CONFIDENTIAL

This document is confidential. Do not disclose or use except as authorized.

the DLT may proceed with nivolumab monotherapy dosing every 4 weeks if considered appropriate by the treating physician.

Adverse events that meet DLT criteria but occur outside the DLT window will be classified as unacceptable AEs and study treatment will be discontinued per Section 5.6.

For the safety lead-in portion of this study, patients are evaluable for DLTs if: 1) they experience a DLT at any time during the DLT evaluation period; or 2) in the absence of DLT have received at least one dose of ipilimumab and one dose of nivolumab, and have completed respective safety assessments without major violations over the entire DLT evaluation period. Patients who are not fully evaluable for DLTs during the DLT evaluation period of 6 weeks following Day 1, will be replaced.

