- AST(SGOT)/ALT(SGPT)  $\leq 3 \times \text{laboratory upper limit of normal (ULN)}$
- Serum creatinine  $\leq 1.5 \times \text{ULN}$   
OR creatinine clearance (measured or calculated)  $\geq 60 \text{ mL/min}$   
for participants with creatinine levels  $> 1.5 \times \text{ULN}$   
*(GFR can be used in place of creatinine or creatinine clearance)*
- Total serum bilirubin  $\leq 1.5 \times \text{ULN}$   
*(except participants with Gilbert's Syndrome, who can have a total bili  $< 5 \times \text{ULN}$ )*
- Resting baseline oxygen saturation  $\geq 92\%$  at rest - by pulse oximetry

CONFIDENTIAL

This document is confidential. Do not disclose or use except as authorized.

**3.1.7** MRI (or CT if MRI contraindicated) within 14 days prior to start of study treatment  
Corticosteroid dose must be stable or decreasing for at least 5 days prior to the scan. If steroids are added or the steroid dose is increased between the date of the screening MRI or CT scan and the start of treatment, a new baseline MRI or CT is required.

**3.1.8** Ability to understand and the willingness to comply with scheduled visits, treatment schedule, laboratory testing, and other requirements of the study, including disease assessment by MRI (or CT), as confirmed by signing a written informed consent document.

**3.1.9** For **Cohort 2**, patients must be a candidate for external beam radiotherapy including either conventional fractionated conformal dosing or stereotactic radiosurgical boost dosing (participants may enroll if they are receiving radiotherapy or have completed it within 12 weeks of starting immunotherapy);

3.1.9.1 For **Cohort 2** patients who are undergoing fractionated conformal re-irradiation to a tumor site that has been previously irradiated, an interval of at least 6 months must have passed since they completed their prior irradiation to be eligible unless the current course of radiation is targeting a new area of tumor growth outside the 80% isodose line of the original radiation field as determined by the treating investigator.

**3.1.10** The effects of nivolumab on the developing human fetus are unknown. For this reason:

3.1.10.1 Women of childbearing potential (WOCBP; defined in Section 3.4) must have a negative serum or urine pregnancy test (minimum sensitivity 25 IU/L or equivalent units of HCG) within 24 hours of starting study therapy;

3.1.10.2 Women must not be breastfeeding;

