### 5.2.1 Safety Lead-In

The safety lead-in will utilize a 3+3 design to determine the MTD/RP2D of ipilimumab when administered with nivolumab following radiation therapy for patients with recurrent/progressive meningioma. Nivolumab will be administered at 3 mg/kg every three weeks with ipilimumab. The initial dose level of ipilimumab will be 1 mg/kg every three weeks and will be administered on the same day as nivolumab. There is extensive existing safety data confirming adequate tolerability of nivolumab administered with ipilimumab at these dose levels. However, since there is no safety data administering these two agents following radiation therapy for recurrent/progressive meningioma patients, the first six patients will be considered a safety lead-in and observed in groups of three for dose limiting toxicities (DLT) for an evaluation period of 42 days (see DLT definitions in Section 5.2.1.1) as follows:

- If at Dose Level 0,  $\leq 1$  of the first 3 patients develop DLT, 3 more patients will be enrolled to Dose Level 0.
- If at Dose Level 0,  $>1$  of the first 3 patients or  $>1$  of the first 6 patients develop DLT, cohort enrollment will be stopped immediately, and re-started from the beginning with 3+3 patients enrolled at a dosing interval of 4 weeks (Dose Level -1).
- If at Dose Level -1,  $>1$  of the first 3 patients or  $>1$  of 6 patients develop DLT, cohort enrollment will be stopped immediately, and re-started from the beginning with 3+3 patients enrolled at a dosing interval of 6 weeks (Dose Level -2).
- If at Dose Level -2,  $>1$  of the first 6 patients develops DLT, the safety lead-in will be discontinued. In this case, a single-arm phase II study of nivolumab monotherapy will be performed.

Dose-limiting toxicities (DLT) will be determined by toxicities related to ipilimumab during or beginning over the first 42 days of treatment as defined below in Section 5.2.2.

Table 5.2.1. Dose levels and doses to be evaluated in safety lead-in.

CONFIDENTIAL

This document is confidential. Do not disclose or use except as authorized.

Dose level	Nivolumab		Ipilimumab	
	Dose (mg/kg)	Frequency	Dose (mg/kg)	Frequency
Zero (0)	3	Every 3 weeks	1	Every 3 weeks
Minus one (-1)	3	Every 4 weeks	1	Every 4 weeks
Minus two (-2)	3	Every 6 weeks	1	Every 6 weeks

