### **6.1 Dose Delay Criteria for Nivolumab and/or Ipilimumab**

Dose delay criteria specified below apply for all nivolumab and/or ipilimumab related adverse events. Nivolumab and ipilimumab must be delayed until treatment can resume (see Section 6.3).

NOTE: Participants who require delay of nivolumab or ipilimumab should be re-evaluated weekly or more frequently if clinically indicated and resume dosing when re-treatment criteria are met.

Nivolumab and ipilimumab administration should be delayed for the following:

- Any Grade  $\geq 2$  non-skin, drug-related adverse event, with the following exceptions:
  - Grade 2 drug-related fatigue or laboratory abnormalities do not require a treatment delay
- Any Grade  $\geq 3$  skin, drug-related adverse event
- Any Grade  $\geq 3$  drug-related laboratory abnormality, with the following exceptions for asymptomatic amylase or lipase, AST, ALT, or total bilirubin:
  - Grade 3 lymphopenia or leukopenia does not require dose delay.
  - Grade  $\geq 3$  amylase or lipase abnormalities that are not associated with symptoms or clinical manifestations of pancreatitis do not require a dose delay. It is recommended to consult with the study's Overall PI, [name], for Grade  $\geq 3$  amylase or lipase abnormalities, and to assess clinically relevant laboratory tests at more frequent intervals to be determined by the investigator.
  - If a participant has a baseline AST, ALT, or total bilirubin that is within normal limits, delay dosing for drug-related Grade  $\geq 2$  toxicity
  - If a participant has baseline AST, ALT, or total bilirubin within the Grade 1 toxicity range, delay dosing for drug-related Grade  $\geq 3$  toxicity

Any adverse event, laboratory abnormality, or intercurrent illness which, in the judgment of the investigator, warrants delaying the dose of study medication.

CONFIDENTIAL

This document is confidential. Do not disclose or use except as authorized.

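### The liver exceptions in Section 5.2.2 can leave a persistent joint AST/ALT and bilirubin elevation uncounted as a DLT, and their order relative to the Grade 2 clause is not stated

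*Combined protocol and SAP*

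**What the plan says.** Section 5.2.2 counts as a DLT any Grade 3 or higher event at least possibly related to ipilimumab in the first 42 days. It then lists events of which "The following exceptions will not be classified as DLT". Three entries matter here:

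- "Grade 3 Immune-related adverse events (irAEs – see definition below) that downgrade to Grade" 2 or lower within 5 days, or to Grade 1 or baseline within 14 days;
- transaminase elevation up to 8 x ULN;
- total bilirubin up to 5 x ULN.

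The first entry has a time limit. The two liver entries have none, and neither mentions the other analyte.

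After the list comes an addition: "DLT will also include grade 2 immune-related adverse events that occur during the DLT period defined above that require interruption of ipilimumab". This clause applies only where the event has failed to reach Grade 1 or lower within 7 days.

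Section 6.4 permanently stops nivolumab plus ipilimumab for a drug-related AST or ALT above 8 x ULN, for bilirubin above 5 x ULN, or for concurrent AST or ALT above 3 x ULN and bilirubin above 2 x ULN. Section 6.3 repeats the stop for combined Grade 2 values that meet the 6.4 limits.

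Under Section 5.2.1, more than 1 DLT among the first 3 or first 6 patients at Dose Level 0 means "cohort enrollment will be stopped immediately, and re-started from the beginning with 3+3 patients enrolled at a dosing interval of 4 weeks".

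**The concern.** Section 5.2.2 mirrors two of the three liver stopping rules in 6.4 and has no counterpart to the third. A joint rise in transaminases and bilirubin is the pattern the protocol treats separately in 6.4 and again in its potential drug-induced liver injury definition (7.2.8). Yet each value, read alone, can sit inside an exception that never expires.

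The Grade 2 clause adds a second difficulty. Section 6.1 says: "If a participant has a baseline AST, ALT, or total bilirubin that is within normal limits, delay dosing for drug-related Grade" 2 or higher. A Grade 2 immune transaminase rise therefore interrupts ipilimumab, and if it lasts beyond 7 days it meets both the clause that makes it a DLT and the exception that says it is not one. Two careful readers could classify the same patient in opposite ways.

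The lead-in exists because, as 5.2.1 says, there are no safety data for this pair of drugs after radiation in these patients. With six patients per level, one classification can decide whether the level passes.

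**Working it through.** **Step 1: compare the liver rules.** The values are illustrative multiples of ULN.

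| AST or ALT | Bilirubin | Inside both 5.2.2 liver exceptions | Permanent stop under 6.4 |
|---|---|---|---|
| 4 | 1 | yes | no |
| 4 | 2.5 | yes | yes |
| 6 | 4 | yes | yes |
| 7.9 | 4.9 | yes | yes |
| 9 | 1 | no | yes |

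The sections agree on single analytes and part only on the joint criterion.

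**Step 2: can such an event be Grade 3?** Yes, on the protocol's own text. Section 6.4 lists the 8 x and 5 x limits as exceptions to its rule that Grade 3 laboratory abnormalities need not stop treatment. The Appendix C hepatotoxicity footnote lets ipilimumab be held, within the same limits, until values return to Grade 2.

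**Step 3: follow a persistent Grade 3 joint event through the plan.**

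- The base rule would count it, but each value falls under a liver exception.
- The exemption for reversible Grade 3 irAEs does not apply, because the event does not reverse in time.
- The consultation route in 5.2.2 is for events below Grade 3 ("except if listed as exempt above), may also be defined as a DLT after a consultation with the Sponsor"), so it is not open.
- The boundary in 14.1.5.2 counts only related non-hematologic events of Grade 4 or higher.
- The patient remains evaluable, having "in the absence of DLT have received at least one dose of ipilimumab and one dose of nivolumab" and completed the safety assessments, and so is not replaced.

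The event can therefore enter the count as a DLT-free patient.

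**Step 4: the order of clauses for Grade 2.** If the exceptions govern, even a lasting Grade 2 joint event does not count. If the Grade 2 clause governs, a lasting Grade 2 elevation counts while a worse Grade 3 elevation within 8 x ULN does not. Neither result looks intended.

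**Step 5: size.** The plan gives no figure to reproduce, and no DLT or liver-event rate. Let c be the per-patient chance of a counted DLT and e the chance of an uncounted joint event, mutually exclusive. Both are assumed. A level passes when at most 1 of 6 patients has a DLT.

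Pass probability under current counting: (1−c)^6 + 6c(1−c)^5. The loss if joint events are counted is this value minus the same expression with c+e in place of c.

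| c | Pass probability now | Loss, e = 1% | Loss, e = 2% | Loss, e = 5% |
|---|---|---|---|---|
| 5% | 0.967 | 0.013 | 0.028 | 0.081 |
| 10% | 0.886 | 0.020 | 0.041 | 0.109 |
| 15% | 0.776 | 0.024 | 0.048 | 0.121 |
| 20% | 0.655 | 0.025 | 0.049 | 0.121 |

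Given that exactly one of six patients has the event, counting it turns a pass into a fail when exactly one of the other five has a counted DLT: 5c(1−c)^4 = 0.204, 0.328, 0.392 and 0.410 for c = 5%, 10%, 15% and 20%, with c the rate among those five.

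The chance that at least one of six patients has the event is 1−(1−e)^6 = 0.059, 0.114 and 0.265 for e = 1%, 2% and 5%.

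**The case against.** The strongest reply is that a 6.4 stop was never meant to equal a DLT. Section 6.4 ends the combination for Grade 3 colitis of any duration, while 5.2.2 exempts a Grade 3 irAE that falls to Grade 2 or lower within 5 days. That is right. A reader might infer that every 6.4 liver stop should be a DLT at any grade. The documents do not support this: a Grade 2 joint event that settles within 7 days is milder than the reversible Grade 3 events the plan deliberately exempts. What remains is the persistent event, which no reversal rule covers.

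A second reply is that 5.2.2 exempts single analytes, so a joint event is not on the list. It could then count under the base rule at Grade 3, or go to consultation below Grade 3. This is a possible reading, but the text does not state it, and the exceptions carry no condition that would exclude a joint rise.

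A third is that the Grade 2 clause comes later and is more specific, so it naturally governs. That is also arguable. But it yields the inversion in Step 4, and the only nearby remark on precedence, in the consultation sentence, leans towards the exemptions and covers only that route.

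The consequences are limited. The patient stops the combination in any case. Events meeting the 7.2.8 definition are reported as SAEs to the Overall PI, so they are not hidden. A failed level lengthens the dosing interval without changing the mg/kg dose. However, no rule turns that report into a DLT, and Section 12.2 names DLT information, not 6.4 stops, among what the DSMC may receive.

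**Conclusion.** The point holds for two things: persistent, ipilimumab-related joint elevations that can go uncounted even at Grade 3, and the unstated order between the liver exceptions and the Grade 2 clause. Both follow from the text and need no assumed rate. It should be fixed, because one patient can decide a level and the repair is cheap.

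The size is modest and rests on assumed rates. The loss in pass probability is at most 1.3 to 2.5 percentage points at an event rate of 1%, 2.8 to 4.9 at 2% and 8.1 to 12.1 at 5%, for c from 5% to 20%. These are upper limits if e is taken as the rate of all joint events: those that reverse quickly would properly stay exempt, and some lasting Grade 2 cases may already count.

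A reader might take the 20% to 41% figure as the chance of a wrong lead-in decision. It is not: it applies only once one patient has had the event.

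**What to change.** Make two changes in Section 5.2.2.

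1. State that the two liver exceptions apply only to isolated elevations. They do not apply when AST or ALT above 3 x ULN and total bilirubin above 2 x ULN occur together and are not explained by Gilbert's syndrome, raised baseline bilirubin or another clear cause. Such events are then judged by the Grade 3 base rule, the existing exemption for rapidly reversible Grade 3 irAEs, and the Grade 2 seven-day clause. The Gilbert's wording is needed because Section 3.1.6 limits bilirubin "except participants with Gilbert's Syndrome, who can have a total bili" below 5 x ULN.
2. State that, for isolated elevations within 8 x and 5 x ULN, the liver exceptions take precedence over the Grade 2 clause. This removes the inversion between Grade 2 and Grade 3.

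Leave the exemption for rapidly reversible Grade 3 irAEs as it stands. Do not make the joint criterion a DLT at any grade, which would collide with that exemption. Do not put Grade 3 irAEs that fall to Grade 2 under the seven-day clause, which would undercut it.

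The cost is a slightly higher chance, within the limits above, that a level fails and the lead-in restarts with up to six patients at a longer dosing interval. The second change also settles that a lasting isolated Grade 2 liver irAE is not a DLT, a choice the sponsor should make knowingly.

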### **5.2.4 Ipilimumab Therapy**

Ipilimumab will be administered every 3 weeks at a dose of 1 mg/kg for 4 consecutive doses, with nivolumab.

CONFIDENTIAL

This document is confidential. Do not disclose or use except as authorized.

Dosing window: There is an administration window of -2/+5 days for Ipilimumab administrations; however, participants may be dosed no less than 24 days (23 non-dosing days) between doses.

Labs/assessments window: Labs/assessments may be performed up to 7 days prior to Ipilimumab doses.

Counting of days will not be continuous on study. In the event of a treatment delay due to a toxicity, the current cycle will be extended until the criteria to resume treatment are met. The day of treatment restart will be the participant's subsequent cycle's Day 1.

If treatment with study medication is delayed > 12 weeks, the participant must be permanently discontinued from study therapy, except as specified in Section 6.4.

Treatment will be administered on an outpatient basis. Reported adverse events and potential risks are described in Section 7. Appropriate dose modifications are described in Section 6. No investigational or commercial agents or therapies other than those described below may be administered with the intent to treat the participant's malignancy.

For details regarding drug storage, preparation, administration, and use time please refer to Section 8 of the protocol and the current BMS-734016 (Ipilimumab) Investigator Brochure.

Ipilimumab is to be administered as an IV infusion over 30 minutes (window of -10 / + 30 min). At the end of the infusion, flush the line with a sufficient quantity of normal saline.

On treatment days when both nivolumab and ipilimumab are administered, nivolumab will be administered first with a 30-minute observation window before starting ipilimumab.

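### At Dose Levels 0 and -1, a lead-in patient can count as DLT-free after only one of the two doses scheduled in the 42-day window

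*Combined protocol and SAP*

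**What the plan says.** Section 5.2.1 sets up a 3+3 lead-in in which patients are "observed in groups of three for dose limiting toxicities (DLT) for an evaluation period of 42 days". A level is abandoned if more than one of the first three, or more than one of six, has a DLT. It therefore clears with zero or one DLT in six. At Dose Level 0, "The initial dose level of ipilimumab will be 1 mg/kg every three weeks and will be administered on the same day as nivolumab". Table 5.2.1 lengthens the interval for both drugs to 4 weeks at Level -1 and 6 weeks at Level -2.

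Section 5.2.2 fixes the window: "The DLT period is considered the first 42 days of study therapy". A patient is evaluable if a DLT occurs at any time in it. Otherwise the patient must "in the absence of DLT have received at least one dose of ipilimumab and one dose of nivolumab" and must "have completed respective safety assessments without major violations over the entire DLT evaluation period". On replacement: "Patients who are not fully evaluable for DLTs during the DLT evaluation period of 6 weeks following Day 1, will be replaced". No second dose is required, and what makes a violation major is not defined.

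Dosing in the window is also governed by Section 6. Section 6.1 begins its list with "Nivolumab and ipilimumab administration should be delayed for the following". Section 6.3 says when dosing may resume, and Section 6.4 says when the combination must stop.

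**The concern.** The lead-in exists because, by Section 5.2.1's own account, there are no safety data for these two drugs after radiation in this population. What it should test is the schedule as given, which at Levels 0 and -1 means two combined doses within the window. If a patient who received one dose enters the 3+3 count as DLT-free, the observed DLT rate describes less exposure than the level prescribes, and the level clears more easily than the rule suggests. Clearing it opens a cohort of about 25 patients.

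**Working it through.** The plan states no operating characteristics for the lead-in, so there is no figure to reproduce.

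**1. Doses scheduled in Days 1 to 42** (intervals from Table 5.2.1)

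| Level | Interval | Dose days | Doses in window |
|---|---|---|---|
| 0 | 21 days | 1, 22, 43 | 2 |
| -1 | 28 days | 1, 29, 57 | 2 |
| -2 | 42 days | 1, 43 | 1 |

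Section 5.2.4 says for ipilimumab that "participants may be dosed no less than 24 days (23 non-dosing days) between doses". If that line governs at Level 0, dose 2 falls on Day 1 + 24 = 25 at the earliest. With the +5-day allowance on Day 22 it falls by Day 27. Both are inside the window, so the one-dose minimum equals planned exposure only at Level -2.

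**2. Who can miss dose 2 and still count as DLT-free**

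Section 5.2.2 already removes many candidates. Non-exempt Grade 3 or higher events related to ipilimumab are DLTs. So are Grade 2 immune-related events that interrupt ipilimumab and do not improve to Grade 1 or lower within 7 days. The remaining routes are these:

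- **Non-toxicity miss.** Nothing in Section 5.2.2 makes dose 2 a condition. Replacement would depend on reading the omission as a major violation.
- **Grade 3 immune-related event that downgrades in time, for example colitis.** It is exempt in 5.2.2 if it falls to Grade 2 or lower within 5 days, or to Grade 1 or baseline within 14 days. Section 6.4 requires the combination to stop for drug-related Grade 3 colitis whatever its duration.
- **AST or ALT above 3 x ULN with bilirubin above 2 x ULN.** This is a stopping criterion in 6.4. It can lie below both DLT thresholds in 5.2.2 (8 x and 5 x ULN).
- **Transaminases up to 8 x ULN.** Exempt in 5.2.2; Section 6.1 delays both drugs from Grade 2 when baseline is normal. A Grade 2 rise still present after 7 days appears to meet both the exemption and the Grade 2 DLT clause, and the text does not say which prevails.
- **Grade 2 diarrhea, colitis or pulmonary toxicity that improves to Grade 1 within 7 days.** It escapes the Grade 2 DLT clause, but Section 6.3 withholds treatment until baseline is reached.

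The delay routes matter only if the delay runs past Day 42. Such a delay is allowed: Sections 5.2.3 and 5.2.4 permit 12 weeks, Sections 6.3 and 6.4 permit 6 weeks, and the general part of Section 6 permits 42 days between doses. Even 42 days between doses puts dose 2 on Day 1 + 42 = 43, outside the window.

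**3. Effect on the chance of clearing a level (illustration)**

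Assumptions: DLT risk q per dose, equal and independent across doses; two-dose risk p = 1 - (1 - q)^2; k of the six counted patients carry only risk q. At most 1 of 6 implies at most 1 of the first 3, so the first-stage rule adds nothing:

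P(clear) = (1 - q)^k (1 - p)^(6 - k) [1 + k q/(1 - q) + (6 - k) p/(1 - p)]

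- q = 0.15: p = 1 - 0.85^2 = 0.2775. With k = 0, 0.1422 + 0.3278 = 0.47. With k = 2, 0.1969 x [1 + 0.3529 + 1.5363] = 0.57.
- q = 0.20: p = 1 - 0.80^2 = 0.36. With k = 0, 0.0687 + 0.2319 = 0.30. With k = 2, 0.1074 x [1 + 0.50 + 2.25] = 0.40.

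**4. Other assumed risks**

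Here p is fixed, and q is set either by equal risk per dose, q = 1 - sqrt(1 - p), or by giving dose 2 twice the risk of dose 1, (1 - q)(1 - 2q) = 1 - p.

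| Two-dose risk p | k = 0 | k = 2, equal risk | k = 2, dose 2 doubled |
|---|---|---|---|
| 20% | 0.655 | 0.733 | 0.762 |
| 33% | 0.358 | 0.461 | 0.506 |
| 50% | 0.109 | 0.182 | 0.224 |

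The direction is the same throughout. The model fits non-toxicity misses best, because patients who miss dose 2 through toxicity are not a random subset.

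**The case against.** A reader might infer that anyone unable to receive dose 2 is counted as DLT-free. The documents do not support that. Many dose-blocking events are DLTs, and Section 5.2.2 lets non-exempt events below Grade 3 be declared DLTs after consultation. Nor does a Grade 2 event that settles within 7 days generally create a one-dose patient. A toxicity delay extends the cycle, and dosing usually resumes at Grade 1 or baseline, so an event present on Day 22 would allow dose 2 by about Day 29. This objection stands, and it limits the point to the routes listed above.

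The size is also hypothetical. The documents give neither a per-dose DLT risk nor a number of one-dose patients, and Section 5.2.1 cites extensive data on tolerability of these doses. Half-lives of 15.4 days (ipilimumab) and 26.7 days (nivolumab) mean that one dose gives lasting exposure, so equal risk per dose is doubtful. A fully exposed 3+3 already clears 30% to 47% of the time at the assumed risks. All of this stands as a limit on the size, but not on the gap in the definition.

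A missed dose might be treated as a major violation. That is possible but unstated, so the rule is ambiguous at best. A one-dose minimum does suit Level -2, and a uniform minimum across levels is understandable, but it does not suit the other two.

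Finally, monitoring continues after the lead-in. Section 14.1.5.2 suspends accrual at 2 of the first 10 patients, or more than 20% afterwards, and the monitoring committee may see DLT data (Section 12.2). That suspension rule counts only related non-hematologic events of Grade 4 or higher, so it is narrower than the DLT rule.

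**Conclusion.** The point holds in a limited form. As written, the evaluability rule lets a patient with half the scheduled doses count as having tolerated Dose Level 0 or -1. This applies when dose 2 is missed for a non-toxicity reason, or for an event that Section 5.2.2 exempts and Section 6 makes grounds to stop or delay. That conclusion rests on the text and on the dose count, not on the probabilities.

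Under the 15% and 20% per-dose assumptions, two one-dose patients among six raise the chance of clearing by about 0.10 (0.47 to 0.57, or 0.30 to 0.40). It would go too far to say that the plan will pass an intolerable level, because the number of one-dose patients is unknown and may be zero. It would also go too far to say that a toxicity-related miss must never count as DLT-free: the exemptions in Section 5.2.2 appear deliberate. What is missing is an explicit statement of how they combine with Section 6. The definition should be changed before lead-in data are counted.

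**What to change.** In Section 5.2.2, define an evaluable patient without a DLT as one who received, within the 42-day window, every dose of both drugs scheduled in that window at the assigned level. By nominal schedule days this is two doses at Levels 0 and -1 and one at Level -2. A delayed dose still given inside the window counts.

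State that a patient who misses a scheduled dose for a non-toxicity reason is replaced, and define a major violation.

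For a dose missed because of a drug-related event that is exempt from DLT, reconcile Section 5.2.2 with Sections 6.1, 6.3 and 6.4, and state in advance how that patient enters the 3+3 count. No particular clinical rule is proposed here.

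The cost is a wording amendment and possibly a few extra lead-in replacements; the documents give no basis for a firmer number.
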